
REFERENCE TREATMENT: There will be no comparator treatment or placebo in this study.
		

CRITERIA FOR EVALUATION:
 
Efficacy: The following efficacy assessments will be performed at scheduled visits during the study:
 

• Growth as measured by recumbent length/height, weight and head circumference

		

NAME OF COMPANY	SUMMARY TABLE	FOR NATIONAL AUTHORITY USE ONLY:
Genzyme Corporation, a Sanofi Company [name]	Referring to Part ..... of the Dossier:  Volume:  Page:  Reference:	
NAME OF FINISHED PRODUCT Myozyme® / Lumizyme® (alglucosidase alfa)		
NAME OF ACTIVE INGREDIENT alglucosidase alfa		

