## 6. INVESTIGATIONAL PLAN

### 6.1 Study Design

This is a multicenter study of patients with infantile-onset Pompe disease who begin alglucosidase alfa treatment prior to 1 year of age. Patients with a confirmed diagnosis of Pompe disease who begin alglucosidase alfa treatment prior to their first birthday will be followed in this study for 10 years. The number of patients followed in this study will not be limited prospectively.

The patient's legal guardian(s) must sign the informed consent form prior to performance of any of the study assessments outlined in [Table 9-1](#).

An independent Data Safety Monitoring Board (DSMB) will review safety information on an ad hoc basis as outlined in the DSMB Charter, which is maintained separately from the study protocol.

An independent Allergic Reaction Review Board (ARRB) will be consulted on an ad hoc basis as outlined in the ARRB Charter, which is also maintained separately from this protocol.

Efficacy will be evaluated in terms of physical growth, as measured by changes in recumbent length/height, weight and head circumference; motor development and function, as measured by changes in the motor subscale of the Bayley Scales of Infant and Toddler Development (Bayley-III) (up to 42 months of age), Gross Motor Function Measure (GMFM-88) and Pompe Pediatric Evaluation of Disability Inventory (Pompe PEDI); and cognitive development, as measured by changes in the cognitive and language subscales of the Bayley Scales of Infant and Toddler Development (Bayley-III) (up to 42 months of age), change in the Brief IQ score of the Leiter International Performance Scale – Revised (Leiter-R) and/or the change in the Nonverbal IQ score of the Leiter International Performance Scale – 3rd Edition (Leiter-3) (starting at the final assessment of the Bayley-III before 42 months of age). As an exploratory objective, the effect of alglucosidase alfa treatment on urinary oligosaccharides (Hex4) will be evaluated. For research purposes only, cross-reacting immunologic material (CRIM) status and GAA mutation will be evaluated.

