### **9.3.5 Safety Laboratory Assessments**

Safety laboratory assessments will be performed pre-infusion at the times specified in [Table 9-1](#). The following chemistry and urinalysis variables will be measured:

- Blood urea nitrogen (BUN), creatinine, glucose, uric acid, calcium, phosphorus, albumin, total protein, sodium, potassium, chloride, bicarbonate, serum glutamic oxaloacetic transaminase (SGOT), serum glutamic pyruvic transaminase (SGPT), alkaline phosphatase, total bilirubin, creatine kinase (CK), and creatine kinase muscle, brain isoform (CK-MB).
- Complete blood count with differential.
- Urine appearance, specific gravity, pH, protein, glucose, ketones, bilirubin, and blood. Microscopy will be performed if clinically indicated.

Analysis of blood and urine samples will be conducted and reported by each participating site's laboratory. The Investigator should review lab reports in a timely manner.

The Investigator must indicate if out of range laboratory values are either clinically significant (CS), or not clinically significant (NCS). It is anticipated that some laboratory values may be

outside of the normal value range due to the underlying disease. As in routine practice the Investigators should use their clinical judgment when considering clinical significance. Clinical significance is defined as any variation in laboratory parameters, which has medical relevance and may result in an alteration in medical care. If CS laboratory changes from Baseline are noted, the changes will be documented on the AE CRF. The Investigator will also assess the relationship of all clinically significant out of range values to alglucosidase alfa as being not related, remote/unlikely, possible, probable, or definite. The Investigator will continue to monitor the patient with additional laboratory assessments until (1) values have reached normal range and/or Baseline, or, (2) in the judgment of the Investigator, out of range values are not related to the administration of alglucosidase alfa or other protocol-specific procedures.

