4.3 PRIMARY ENDPOINT(S) ANALYSIS

4.3.1 Definition of endpoint(s)

Physical growth

The endpoints for physical growth are defined as changes from baseline to study time points in recumbent height/length, weight, and head circumference. Changes in Z-scores (standardized age and gender adjusted values) for height/length, weight, and head circumference based on Center for Disease Control (CDC) Growth Charts will also be calculated. Refer to protocol Section 9.2.1 for the details of measurement. Also refer to [Section 5.2](#) for the rationale to incorporate World Health Organization (WHO) growth charts for children <24 months of age.

Motor development

Motor development and function is measured by changes in the motor subscale of the Bayley Scales of Infant and Toddler Development (Bayley-III) (up to 42 months of age), Gross Motor Function Measure (GMFM-88), and Pompe Pediatric Evaluation of Disability Inventory (Pompe PEDI). Change from baseline to study time points will be calculated for the following parameters:

- Bayley-III: raw scores, scaled scores, and composite scores reported for each of the 3 administered scales (cognitive, language, and motor) for patients from 1 month to 42 months of age.
 - The Language scale includes the Receptive and Expressive subtests
 - The Motor scale includes the Fine Motor and Gross Motor subtests
- GMFM-88: total raw score, total score (average of dimension percentage scores) and dimension scores of 5 dimensions (lying and rolling; sitting; crawling and kneeling; standing; walking, running, and jumping). GMFM-88 summary score will be calculated as described in protocol Section 9.2.2.3.
- Pompe PEDI: scores (raw, scaled, normative standard) by scale (functional skills, caregiver assistance) and domain (self-care, mobility, social function)

Refer to protocol Section 9.2.2 for the definitions and measurement details of Bayley-III, GMFM-88 and Pompe PEDI.

Cognitive function

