4.7.3 Additional safety assessments

4.7.3.1 Laboratory variables, vital signs, physical examinations (PE), and electrocardiograms (ECGs)

The following laboratory variables, vital signs, physical examinations (PE), and electrocardiogram (ECG) variables will be analyzed.

- Hematology:
 - Complete blood count with differential
- Clinical chemistry:
 - Metabolism: glucose, total protein, albumin, creatine kinase (CK), creatine kinase MB (creatine kinase muscle, brain isoform [CK-MB]), creatine kinase MB/total creatine kinase
 - Electrolytes: sodium, potassium, chloride, calcium, phosphorus, bicarbonate
 - Renal function: creatinine, blood urea nitrogen (BUN), uric acid (urate)
 - Liver function: alanine aminotransferase (ALT) [serum glutamic pyruvic transaminase (SGPT)], aspartate aminotransferase (AST) [serum glutamic oxaloacetic transaminase (SGOT)], alkaline phosphatase, total bilirubin

- Urinalysis:
 - Urinalysis for quantitative analysis: urine appearance, specific gravity, pH, protein, glucose, ketones, bilirubin, and blood.
 - Microscopy will be performed if clinically indicated.
- Vital signs: heart rate, systolic and diastolic blood pressure, respiratory rate, and temperature
- PE body systems: General Appearance, Skin, HEENT, Lymph Nodes, Heart, Lungs, Breasts, Abdomen, External Genitalia, Pelvic, Rectal, Extremities/Joints, Neurological, Mental Status examinations
- 12-lead ECG variables:
 - Intervals and measurements: heart rate, RR, PR, QRS duration, QRS axis, QT, QTc (Bazett and Fridericia correction)
 - Findings: sinus rhythm, LVH, RVH, conduction abnormalities

For summary tables, data below the lower limit of quantitation/detection limit (LLOQ) will be replaced by half of the LLOQ, while data above the upper limit of quantification (ULOQ) will be replaced by ULOQ value.

Analyses of quantitative variables

For all laboratory variables and quantitative ECG variables (intervals and measurements) above, descriptive statistics for results and changes from baseline will be provided for each planned visit during the on-treatment period. Vital signs data will be provided in a listing.

PE findings

PE findings (normal, abnormal, not examined) for each body system will be presented in a listing.

Analyses of ECG findings

For ECG, the incidence of patients with at least one abnormal ECG during the treatment-emergent period will be summarized according to the following baseline status categories:

- Normal/missing
- Abnormal

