5.2 APPENDIX 2 CHANGES TO PROTOCOL-PLANNED ANALYSES

Regarding the calculation of z-scores for physical growth (recumbent length/height, weight, head circumference) the protocol referred to Center for Disease Control (CDC) Growth Charts. However, the CDC website recommended the World Health Organization (WHO) growth charts for children <24 months of age. If possible, we will incorporate this recommendation. In addition, percentiles of these measurements will be calculated as well.

It was planned to use longitudinal repeated measures modeling to analyze trends in key growth and development parameters over time; however, as out of the 12 patients enrolled 7 patients had withdrawn or died in less than 4 years, this analysis is not likely to be informative and will be omitted.

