5.4.3 Analysis windows for time points

The following analysis windows will decide how the scheduled and/or unscheduled visits will be used in the by-visit analyses of efficacy, safety, and exploratory variables.

A measurement (scheduled or unscheduled) will be used if it is available and measurement date is within the analysis window.

After applying these time windows, if multiple assessments are associated to the same time point, the closest from the targeted study day will be used. Except where specified otherwise, if the difference is a tie, the value after the targeted study day will be used. If multiple valid values exist within a same day, then all the valid values of the day will first be averaged before applying the

aforementioned rules. (Note that the rule of using the later date of the window does not conflict with any protocol-specified procedure that has to be done pre-infusion (eg, IgG assessments), as all IgG assessments will be performed prior to infusion unless there was a protocol deviation.)

If there is no measurement for a given parameter in an analysis window, data will be considered missing for the corresponding visit.

Efficacy assessments

The schedule for the efficacy assessments is shown in the following table.

Efficacy assessments	Schedule
Recumbent length/height, weight, and head circumference	Every 3 months age < 3 years; every 6 months 3 to <5 years, every 12 months \geq 5 years
Bayley-III	every 6 months ages 1 month to 42 months
Leiter-R/Leiter-3	from final Bayley-III assessment < 42 months of age, every 12 months
GMFM-88	every 6 months age < 5 years; every 12 months \geq 5 years
Pompe PEDI	every 6 months age < 5 years; every 12 months \geq 5 years

Given that patients enter study at different ages, if we define analysis windows for the efficacy endpoints based on the assessment schedule, the definitions will vary depending on each patient's age at study entry. In addition, due to the small patient population, we will focus on individual patient growth by age. The following analysis windows for efficacy assessments will not be used in by-visit summary tables or figures, but may be used in the patient listing to associate observations to the nearest study visits.

Maximum age at signing of the informed consent was 1.9 years.

Table 7 - Analysis window definition for recumbent length/height, weight, and head circumference

Scheduled visit post baseline	Targeted study day	Analysis window in study day

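### The by-visit raw-change tables for laboratory values and ECG intervals cannot separate normal maturation from a safety effect; range-based summaries should be added beside them.

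*SAP*

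**What the plan says.** SAP 4.7.3.1, under the analyses of quantitative variables, states for laboratory variables and ECG intervals and measurements that "descriptive statistics for results and changes from baseline will be provided for each planned visit during the on-treatment period". It states no age adjustment, reference-range shift or scaling to the ULN for these tables.

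The setting is as follows:

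- **Age at entry.** SAP 5.4.3: "Maximum age at signing of the informed consent was 1.9 years".
- **Follow-up.** Protocol 6.1: patients "will be followed in this study for 10 years".
- **Control.** Protocol synopsis: "There will be no comparator treatment or placebo in this study".
- **Laboratory.** Protocol 9.3.5: "Analysis of blood and urine samples will be conducted and reported by each participating site's laboratory". Neither document states a harmonisation rule for chemistry, hematology or urinalysis.
- **Attrition.** SAP 5.2: "out of the 12 patients enrolled 7 patients had withdrawn or died in less than 4 years".

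Other safety outputs are also planned. SAP 4.7.3.1 gives the incidence of patients with at least one PCSA for laboratory values, vital signs and ECG intervals. It also gives the incidence of abnormal ECGs by baseline status, with normal and missing baselines in one category. Under protocol 9.3.5 the investigator classes each out-of-range value as clinically significant or not, and clinically significant changes go on the adverse event form.

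For growth, SAP 4.3.1 adds "Changes in Z-scores (standardized age and gender adjusted values) for height/length, weight, and head circumference". SAP 5.4.3 also drops by-visit summaries of efficacy, because patients enter at different ages and are few, and turns to individual growth by age.

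**The concern.** Many analytes, heart rate and ECG intervals can be expected to move as an infant becomes a school-age child. That is general knowledge; the documents do not quantify it. In a single-arm study, a mean raw change over such a span adds maturation, disease course and any drug effect together, and nothing in the table separates them. An expected change can hide an unexpected one, or can be mistaken for a signal.

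The SAP accepts this reasoning for efficacy: it age-standardises growth and gives up by-visit efficacy summaries. The laboratory and ECG data come from the same children, with the same spread of ages and the same attrition, yet they keep pooled by-visit raw changes and no reason is given.

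Long-term safety is the study's secondary objective (SAP Table 2), so these tables should be readable. No formal test or decision rule depends on them.

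**Working it through.** The documents state no sample size, power or expected change, so there is no planned figure to reproduce.

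**1. Age span of the change.** Age at visit = age at entry + study day / 365.25. The target day for Week 520 in the SAP's efficacy windows is 3650, and 3650 / 365.25 = 9.99 years. A patient entered near birth would be about 10.0 years old, and one entered at 1.9 years about 1.9 + 9.99 = 11.9 years old. (The 1.9 years is age at consent; I take it as age at baseline.)

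**2. How many patients can show that span.** 12 - 7 = 5, so at most 5 of 12 (42%) contribute from year 4 on. For the other 7, change stops below about 1.9 + 4 = 5.9 years of age. Later columns therefore rest on a different and smaller group than earlier ones.

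**3. Laboratory differences.** Assume each laboratory has a constant additive offset with SD b, in units of the within-laboratory SD, with b from 0.25 to 1.0 (assumption). The offset's share of variance is:

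| Quantity | Formula | b = 0.25 | b = 0.5 | b = 1.0 |
|---|---|---|---|---|
| Pooled raw result | b²/(1 + b²) | 6% | 20% | 50% |
| Change, same unchanged laboratory | offset cancels | 0% | 0% | 0% |
| Change, laboratory or assay switched | 2b²/(2 + 2b²) | 6% | 20% | 50% |

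So under this model the laboratory problem affects pooled raw results, and affects changes only when a patient's laboratory or assay changes. It does not touch the ECG, which protocol 9.3.4 has a site cardiologist review.

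**4. QTc under Bazett.** QT = QTcF × RR^(1/3) and QTcB = QT / RR^(1/2), so QTcB = QTcF × RR^(-1/6) with RR = 60 / heart rate. Take QTcF constant at 400 ms and heart rate falling from 120-140 to 80-100 bpm (assumptions):

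| Heart rate (bpm) | QTcB (ms) | Change (ms) |
|---|---|---|
| 120 to 100 | 449.0 to 435.5 | -13.4 |
| 130 to 100 | 455.0 to 435.5 | -19.5 |
| 120 to 90 | 449.0 to 428.0 | -21.0 |
| 130 to 85 | 455.0 to 423.9 | -31.1 |
| 140 to 80 | 460.7 to 419.6 | -41.0 |

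(Changes are from unrounded values; subtracting the rounded ones gives -13.5 in the first row.) The range is about -13 to -41 ms with QTcF unchanged. The direction follows from the formula whenever heart rate falls; the size depends on the assumed rates.

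**5. Does the PCSA table fill the gap?** SAP 4.7.3.1 bases it on the worst value in the treatment-emergent period and counts patients regardless of baseline level. Protocol 9.3.5 anticipates values outside the normal range because of the underlying disease. A patient already beyond a limit at baseline can therefore be counted the same way as one who newly crosses it, and the table has no time course. SAP 5.4.2 shows that some criteria involve a normal range or a change from baseline, which helps in part. Whether the limits are age-specific depends on a sponsor document that is not part of the protocol or SAP.

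**The case against.** The case against has four parts.

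**Other outputs exist.** A reader might infer that the laboratory and ECG analyses as a whole mainly show maturation and laboratory differences rather than safety. The documents do not support that. PCSA incidence, abnormal-ECG incidence, listings and the adverse event route are all planned, and with 12 patients individual review is feasible. Nor can the word mainly be backed by any figure in the documents. This stands, and it confines the point to the by-visit tables. It does not remove the point, because none of those outputs shows movement against a reference range by visit.

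**Bazett is not alone.** A reader might infer that a true QT prolongation would be lost. It would not: SAP 4.7.3.1 tabulates Fridericia, QT, RR and heart rate beside Bazett, and protocol 9.3.4 requires both corrections. What remains is a note on which column to read for change.

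**Reach.** A constant additive laboratory offset cancels within a patient, and at most 5 of 12 patients can cover the long age span. Both stand.

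**The protocol asks for raw change.** Protocol section 11 plans summary statistics for change in laboratory parameters from baseline. Moving those to listings would drop a protocol-planned analysis. This stands, so the remedy has to be an addition. The objection that shift tables will be sparse after year 4 also stands, but it applies equally to the planned means.

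**Conclusion.** The point holds for the by-visit raw-change tables. With no comparator, no age standardisation and an age span from 1.9 years or younger to about 10.0-11.9 years in patients who complete, they cannot distinguish maturation from a safety effect. Pooled raw laboratory results also mix site laboratories, while changes do so only if a patient's laboratory or assay changes. The PCSA table relieves this only partly.

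The overall size of the problem cannot be computed from the documents. The QTcB figure of about -13 to -41 ms illustrates it and rests on the assumed heart rates and a constant QTcF of 400 ms; the 6% to 50% laboratory share rests on an assumed additive offset. Because all safety analyses are descriptive and other safety outputs exist, this is a minor improvement, not a defect that invalidates the safety evaluation.

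**What to change.** In SAP 4.7.3.1, keep the raw-change summaries and add:

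1. Low/normal/high shift summaries, baseline to visit or baseline to worst value, against the reporting laboratory's age- and sex-specific range.
2. CK, CK-MB, ALT and AST as multiples of that laboratory's ULN.
3. Preferably, per-patient plots by age for the main laboratory and ECG variables, to match the efficacy approach.
4. A sentence keeping both QTc corrections, noting that QTcB is expected to fall as heart rate falls, and stating that change is read from the QTcF column.
5. A statement of whether the PCSA limits are age-specific.

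The cost is mostly programming. Sites already judge results as in or out of range, and the PCSA rules already call on normal ranges. The documents do not show that age- and sex-specific ranges were stored throughout, so results without one will be missing from the new summaries, and the number missing should be shown. Counts after year 4 will come from at most 5 patients. Because the raw laboratory changes stay, no protocol-planned analysis is lost.

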#### 4. INTRODUCTION

Pompe disease is a rare autosomal recessive metabolic muscle disease caused by the deficiency of acid  $\alpha$  glucosidase (GAA), an enzyme that degrades lysosomal glycogen. As opposed to the exclusively cytoplasmic accumulation of glycogen that occurs in other glycogen storage disorders, Pompe disease is characterized by organelle bound (lysosomal) and extra-lysosomal accumulation of glycogen in many body tissues, ultimately leading to multisystemic pathology.

Historically, Pompe disease has been arbitrarily classified into different subtypes based on the age at onset of symptoms, extent of organ involvement, and rate of progression to death. Essentially, there is a broad spectrum of disease ranging from a rapidly progressive form (infantile-onset) to a more slowly progressive form (late-onset) with considerable variability and overlap existing between these extremes (Chen, 2000, *Mol Med Today*; Hirschhorn, 2001, *The Metabolic and Molecular Bases of Inherited Disease*; van den Hout, 2003, *Pediatrics*). It is important to note that all presentations of Pompe disease share a common underlying pathology; i.e., deficiency of GAA with subsequent accumulation of glycogen.

At the most rapidly progressive end of the disease spectrum are patients with the infantile-onset form of Pompe disease. These patients typically present with symptoms within the first 12 months of life. A massive deposition of glycogen in the heart and skeletal muscle results in rapidly progressive cardiomyopathy and generalized muscle weakness and hypotonia.

Moreover, motor development is often completely arrested, or if motor milestones are achieved, they are subsequently lost. Death from cardiac and/or respiratory failure generally occurs before most patients reach 1 year of age (Hirschhorn, 2001, *The Metabolic and Molecular Bases of Inherited Disease*). Patients presenting with this typical disease course have been described in the literature as having 'classical' infantile-onset Pompe disease. A subset of patients with infantile-onset Pompe disease that survive beyond 1 year has been described by Slonim and colleagues (Slonim, 2000, *J Pediatr*). The clinical course of disease in these patients is characterized by a slower progression of cardiomyopathy and longer survival, with patients generally developing respiratory failure between 1 and 2 years of age. Although some patients die before 1 year of age, others may survive beyond 2 years.

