Analyses according to PCSA

Potentially clinically significant abnormality (PCSA) analyses will be performed based on the PCSA criteria defined in Sanofi business and technical document BTD-009536, in effect at Sanofi at the time of the database lock.

Analyses according to PCSA will be performed based on the worst value during the treatment-emergent period, using all measurements (whether local or central, scheduled, nonscheduled or repeated).

For laboratory variables, vital signs, and ECG variables (intervals and measurements) above, the incidence of patients with at least one PCSA during the treatment-emergent period will be summarized regardless of the baseline level.

4.7.3.2 *Neuroimaging Assessment*

As described in protocol Section 9.3.1, serial brain MRIs will be conducted at the discretion of the Investigator as sedation for this procedure may be required for young patients and may pose an unacceptable risk in patients who have cardiopulmonary involvement. MRIs will be conducted according to standard procedures (specified in the study manual [SM]) at the times specified in protocol Table 9-1 in order to evaluate possible changes in brain structures over time.

Neuroimaging assessments will be presented in a listing.

4.7.3.3 *Hearing Testing*

As described in protocol Section 9.3.2, hearing will be assessed at the times specified in protocol Table 9-1 using an age-appropriate method of hearing assessment, as determined by the Investigator.

Hearing testing results will be presented in a listing.

4.7.3.4 *Visual Screening*

Ophthalmologic evaluation is to be performed by the Investigator in accordance with the guidelines described by the American Association of Pediatrics (AAP, 1996, *Pediatrics*). The type of visual screening will be determined by the patient's age at the time of the assessment. All patients will have an exam of the eye, test ocular motility and the red reflex exam. Patients 3 years of age and over will have the same assessments described previously plus a visual acuity test. Patients 4 years of age and over will have each of the previously described assessments plus fundoscopy.

Visual screening results will be presented in a listing.

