5.4.2 Handling of lab data

Handling of potentially clinically significant abnormalities

For PCSAs with 2 conditions, one based on a change from baseline value or a normal range and the other on a threshold value, with the first condition being missing, the PCSA will be based only on the second condition.

For a PCSA defined on a threshold and/or a normal range, this PCSA will be derived using this threshold if the normal range is missing; eg, for eosinophils the PCSA is >0.5 GIGA/L or > ULN if ULN \geq 0.5 GIGA/L. When ULN is missing, the value 0.5 should be used.

Measurements flagged as invalid by the laboratory will not be summarized or taken into account in the computation of PCSA values.

Handling of ADA titer with missing or non-numerical values

If the ADA titer is reported as “<value”, then the limit value will be used for summary tables. For example, if a value is reported as “<100”, 100 will be used for the data point in the calculation of the summary statistics. The respective listings will however still report the original data, eg, <100. No imputation will be performed for missing values.

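### Splitting the PCSA table by baseline status, and giving missing baseline ECGs their own row, would separate abnormalities new since study entry from those already present

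*SAP*

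**What the plan says.** SAP 4.7.3.1 takes each patient's most extreme on-treatment reading: "Analyses according to PCSA will be performed based on the worst value during the treatment-emergent period, using all measurements". For laboratory variables, vital signs and quantitative ECG variables, "the incidence of patients with at least one PCSA during the treatment-emergent period will be summarized regardless of the baseline level". No PCSA table by baseline status is planned. The criteria themselves are in a sponsor document that the SAP cites but does not reproduce.

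SAP 5.4.2 shows that some criteria can look at baseline. It covers the case "For PCSAs with 2 conditions, one based on a change from baseline value or a normal range and the other on a threshold value". If the first condition is missing, the threshold alone decides.

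ECG findings are handled differently in the same section: "the incidence of patients with at least one abnormal ECG during the treatment-emergent period will be summarized according to the following baseline status categories". There are two categories, and the first is "Normal/missing"; the other holds abnormal baselines.

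For laboratory and quantitative ECG variables, "descriptive statistics for results and changes from baseline will be provided for each planned visit during the on-treatment period". Vital signs otherwise go into a listing only.

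On what to expect at entry, Protocol 9.3.5 says: "It is anticipated that some laboratory values may be outside of the normal value range due to the underlying disease". Protocol 4 says of untreated infantile-onset disease: "A massive deposition of glycogen in the heart and skeletal muscle results in rapidly progressive cardiomyopathy".

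**The concern.** Long-term safety is the secondary objective (SAP Table 2). A reader of a table headed by the treatment-emergent period will tend to take its counts as abnormalities that arose on study. A value that was beyond the threshold at entry and stayed there is counted in the same way as one that crossed it in year 5.

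Elsewhere the plan does make this distinction. Protocol 9.5 does not treat pre-existing laboratory abnormalities as adverse events unless they recur after recovery or are clinically significantly exacerbated. SAP 4.7.2 confines treatment-emergent events to those that arise, worsen or turn serious on treatment. The ECG-findings table is split by baseline status. The PCSA table has no such split.

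The ECG-findings table raises a smaller question. A patient with no baseline ECG shares a row with patients known to be normal, and that row is the natural place to look for new abnormality.

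**Working it through.** The plan states no incidence, sample size or power on this point, so there is no figure of its own to reproduce. What follows is illustrative arithmetic on the enrolled count, then a comparison of the planned outputs.

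**Inputs**
- N = 12 patients enrolled (SAP 5.2). I assume all 12 are in the denominator. The number in the full analysis set is not given, and a smaller denominator makes each patient weigh more.
- b = patients with a persistent abnormality at study entry that meets a threshold-only criterion. Not in the documents; I use 3, 6 and 9.
- q = chance of a new abnormality in a patient without one at entry. Not in the documents; I use 0 and 10%.

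**PCSA table**

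Expected reported count = b + (N − b) × q. One patient contributes 1/12 = 8.3 points.

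| b | Reported if q = 0 | Reported if q = 10% | New since entry if q = 10% |
|---|---|---|---|
| 3 | 3/12 = 25% | 3 + 9 × 0.1 = 3.9, or 32.5% | 0.9 patients |
| 6 | 6/12 = 50% | 6 + 6 × 0.1 = 6.6, or 55% | 0.6 patients |
| 9 | 9/12 = 75% | 9 + 3 × 0.1 = 9.3, or 77.5% | 0.3 patients |

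With q fixed at 10%, the reported figure runs from 32.5% to 77.5% as b changes. The planned table cannot show which part of its count is b.

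This applies where the criterion is a threshold alone, or where the baseline condition is missing and SAP 5.4.2 falls back to the threshold. A criterion with a working change-from-baseline condition would not normally be met by a stable pre-existing value.

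**What else shows new abnormality**

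| Data | Change-from-baseline table | PCSA table | Listing |
|---|---|---|---|
| Laboratory | yes, by visit | yes, not split | yes |
| Quantitative ECG | yes, by visit | yes, not split | yes |
| Vital signs | no | yes, not split | yes |

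The by-visit tables describe the group and do not show how many patients crossed a threshold. For vital signs the PCSA table is the only summary table.

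**ECG-findings table**

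Known-abnormal baselines have their own row, so only missing baselines can be misplaced. One patient with a missing baseline and an old abnormality adds 1/n to the pooled row, where n is the number in that row:
- 11 normal + 1 missing: 1/12 = 8%
- 4 normal + 1 missing: 1/5 = 20%
- 2 normal + 1 missing: 1/3 = 33%

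These compositions are assumed. Protocol Table 9-1 schedules a baseline ECG for every patient, and the number missing is not stated, so it may be zero.

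**The case against.** The strongest reply is that this is a choice of presentation. The SAP says openly that baseline is disregarded, so the table counts any on-treatment abnormality and does not claim new onset. Other outputs do use baseline. Clinically significant changes from baseline in laboratory values and ECG are recorded as adverse events (Protocol 9.3.4 and 9.3.5), as is clinically significant worsening in general (Protocol 9.5). They therefore reach the adverse event tables. Safety data are also listed by patient, and with 12 patients a reader can look up each baseline. Pooling missing with normal ECGs is labelled as such, and it errs towards showing a possible new finding. Much of this stands. It limits the point to one of clarity, but it leaves the reader to rebuild by hand a split that the sponsor could print, and it does not give vital signs another summary table.

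A reader might infer more than the documents support:
- That the PCSA analysis ignores baseline altogether. SAP 5.4.2 shows that some criteria can include a change from baseline; which ones do is in the unseen sponsor document.
- That PCSA incidence mainly restates baseline disease, for example through CK or transaminases. Nothing in the documents gives the criteria or the number of patients beyond them at entry.
- That a missing baseline ECG is more likely abnormal than normal, so the pooled row is inflated. Protocol 4 describes cardiomyopathy in the untreated disease, but also reports that treatment reversed its indices in the large majority of infantile-onset patients. Patients may enter already treated, up to 24 months of age (Protocol 7.1), and no document says that any baseline ECG is missing.

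**Conclusion.** The point holds as a cheap improvement. For threshold-only criteria, and for those that fall back to the threshold, the planned PCSA table cannot separate abnormalities new since study entry from those already there. Each persistent one can add 8.3 points at a denominator of 12. The total effect is unknown, because neither the criteria nor the baseline counts are in the documents; the 25%, 50% and 75% above rest on assumed counts. Vital signs are the most exposed, having no other summary table. In the ECG-findings table the effect is confined to missing baselines and is nil if there are none. Safety analyses are descriptive with no testing planned (SAP 4.7), so only interpretation is affected.

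**What to change.** In SAP 4.7.3.1, keep the overall PCSA row and add n/N by baseline PCSA status: no, yes, missing. For criteria with a change-from-baseline condition, state how baseline status is assigned, for example by the threshold part alone. Replace the two ECG baseline categories with Normal, Abnormal and Missing.

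Add a footnote that the no row means new since study entry, not since first treatment. SAP 4.1 starts the on-treatment period at the first in-study infusion even for patients treated earlier.

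Baseline laboratory tests, vital signs and ECG are already scheduled for every patient (Protocol Table 9-1), so no visit or procedure changes. The cost is SAP wording and a few more table rows. Those rows will be small, which is why n/N should be shown and not percentages alone.
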